6.3.2 Off-Site SAE Reporting

When participating in multicenter clinical trials, Principal Investigators may receive “off-site” reports (e.g., SAE Report). These are Sponsor reports of SAEs which occurred at other sites for the same trial, or in different trials using the same test article, that met the criteria for reporting to a regulatory agency. These should be reported to the reviewing IRB per their established reporting procedures. The IRB may require a revision to the ICF and re-consenting of subjects if the SAE provides new information regarding risk to the study subject.

6.3.3 Reporting of Complaints for STAAR Surgical Products

All information collected on a CRF could potentially be identified as a product complaint, as defined in Section 6.1.3. During clinical monitoring by the Sponsor/designee, the information collected on the CRFs will be evaluated to determine if any of the information should be forwarded to the Sponsor for consideration as a complaint according to STAAR standard operating procedures for complaint handling. The Sponsor has the responsibility for evaluating and investigating potential complaints in accordance with STAAR’s internal complaint handling procedures.

Any complaints, malfunctions or similar events related to ancillary STAAR Surgical marketed products used in this study should be reported by the Investigators in accordance with the reference information provided on the commercial packaging.

6.3.4 Adverse Events and SAEs at Subject Exit

Ongoing ocular AEs at study exit will be documented as such in the CRFs and followed per the Investigator’s standard of care.

Ongoing SAEs and ADEs will be followed until resolution or no further change in the condition is expected. Non-serious AEs that are ongoing at the study exit visit or upon discontinuation from the study will be followed per the Investigator’s standard of care. Documentation in the eCRF of this follow-up is not required although subject care should continue as appropriate.

7.0 STATISTICAL METHODS

7.1 Hypothesis

Based on clinical experience with stabilization of lens rotation over time, it is assumed that between 18 and 24 months postoperative, no more than 2% of eyes will exhibit rotation $>5^\circ$. Our null and alternate hypotheses are as follows:

H_0 (null hypothesis): $>10\%$ of eyes with $>5^\circ$ rotation

H_a (alternative hypothesis): $\leq 10\%$ of eyes with $>5^\circ$ rotation

7.2 Study Endpoints

7.2.1 Primary Effectiveness Endpoint

The primary endpoint for this study is rotation of less than or equal to five degrees between 18 and 24 months postoperative. The endpoint will be met if at least 90% of the treated

eyes rotate less than or equal to five degrees between 18 and 24 months postoperative (i.e., $\leq 10\%$ of eyes exhibit $>5^\circ$ rotation).

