Age	Minimum ECD ACD ≥ 3.0mm	Minimum ECD ACD ≥ 3.2mm	Minimum ECD ACD ≥ 3.5mm																										
21-25	3875 cells/mm ²	3800 cells/mm ²	3250 cells/mm ²																										
26-30	3425 cells/mm ²	3375 cells/mm ²	2900 cells/mm ²																										
31-35	3025 cells/mm ²	2975 cells/mm ²	2625 cells/mm ²																										
36-40	2675 cells/mm ²	2625 cells/mm ²	2350 cells/mm ²																										
41-45	2350 cells/mm ²	2325 cells/mm ²	2100 cells/mm ²																										
>45	2075 cells/mm ²	2050 cells/mm ²	1900 cells/mm ²																										
Duration of treatment	Eligible subjects who are enrolled in the study will be seen for 11 study visits over the course of approximately 27 months.																												

Study parameters
	
The study will evaluate:
 
 • Rotational stability as determined through objective methods • Refractive and visual outcomes • Safety 
Primary effectiveness endpoint:
 
 • Rotation of less than or equal to five degrees between 18 and 24 months postoperative. 
Primary effectiveness endpoint success criteria:
 
 • At least 90% of the treated eyes rotate less than or equal to five degrees between 18 and 24 months postoperative (i.e., $\leq 10\%$ of eyes exhibit $>5^\circ$ rotation). 
Secondary effectiveness endpoints include:
 
 • Absolute rotation between visits. • Absolute rotation <5 degrees, <10 degrees, <20 degrees, and <30 degrees from the intended orientation at each visit. • Absolute rotation from the intended orientation at each visit. • Postoperative manifest refraction spherical equivalent and cylinder at each visit. 
Safety Endpoint:
 
 • Ocular AE rates assessed in implanted eyes. 
There are no prespecified performance targets for the secondary endpoints or the safety endpoint.

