
Statistical methods
	
Based on clinical experience with stabilization of lens rotation over time, we assume that between 18 and 24 months no more than 2% of eyes will exhibit rotation $>5^\circ$. Our null and alternate hypotheses are as follows:
 
H_0 (null hypothesis): $>10\%$ of eyes with $>5^\circ$ rotation H_a (alternative hypothesis): $\leq 10\%$ of eyes with $>5^\circ$ rotation
 
[REDACTED]
 
[REDACTED] Rates of rotation of the TICL of <10, <20 and <30 degrees from the intended orientation will be reported.
 
To allow for 10% attrition annually, a total of 124 subjects (up to 248 eyes, with 124 being primary) will be enrolled for assessment of the primary and secondary effectiveness/safety endpoints.
 
[REDACTED]
 
[REDACTED]

	
A sample of 100 eyes provides 94.9% power to reject the null hypothesis that >10% of eyes will exhibit >5° rotation. The two-sided 95.0% upper confidence limit of the proportion of eyes with >5° absolute rotation is ≤ 0.1. The null hypothesis will be rejected if the two-sided 95.0% upper confidence limit of the proportion of eyes with >5° absolute rotation between 18 and 24 months is ≤ 0.1. To allow for losses of 10% per year, a total of up to 124 primary eyes of 124 subjects will be enrolled.

--	---

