7.2.2 Secondary Endpoints

The following additional endpoints will be evaluated:

- Absolute rotation between visits.
- Absolute rotation <5 degrees, <10 degrees, <20 degrees, and <30 degrees from the intended orientation at each visit.
- Absolute rotation from the intended orientation at each visit.
- Postoperative manifest refraction spherical equivalent and cylinder at each visit.
- Ocular AE rates assessed in implanted eyes.

There are no pre-specified performance targets for the secondary endpoints.

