7.4 Sample Size

A sample of 100 eyes provides 94.9% power to reject the null hypothesis that $>10\%$ of eyes will exhibit $>5^\circ$ rotation. We assume that the rotational failure rate will be 2% or less. To allow for losses of 10% per year, a total of up to 124 primary eyes of 124 subjects will be enrolled. If a primary eye of an enrolled subject is explanted during the study, the enrolled fellow eye of that subject may be used in its place for the primary analysis. If the fellow eye was not enrolled or implanted, it may not be used in the primary analysis.

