7.5 Statistical Analysis

The two-sided 95.0% upper confidence limit of the proportion of eyes with $>5^\circ$ absolute rotation will be calculated. The null hypothesis will be rejected if the two-sided 95.0% upper confidence limit of the proportion of eyes with $>5^\circ$ absolute rotation between 18 and 24 months is ≤ 0.1 . An exact binomial confidence interval will be used.

Secondary endpoints, degrees of rotation between visits and misalignment from the intended orientation will be analyzed using descriptive statistics. Rates of rotation of the TICL of <10 , <20 and <30 degrees from the intended orientation will be reported.

Evaluation of study endpoints will be conducted separately for study visits conducted within the protocol defined visit windows and separately for those outside of the visit windows. Out of window visits will be identified during analysis of study accountability. If separate evaluations of in-window and out-of-window data, including the distribution of times outside of the window that data were collected, justify poolability, then the endpoints will be analyzed using the pooled data.

To verify poolability of data across sites, outcomes for the primary endpoint by site will be compared using a 0.15 alpha to test for differences in the primary endpoint among sites. If differences are found, data will be summarized separately by site and possible reasons for the finding will be investigated.

To allow for 10% attrition annually, a total of 124 subjects (up to 248 eyes, with 124 being primary) will be enrolled for assessment of the primary and secondary effectiveness/safety endpoints.

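### Section 7.2.1 and the synopsis declare success on an observed 90%, while section 7.5 requires a confidence limit; with 5 to 10 failures in 100 eyes the two give opposite answers

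*Combined protocol and SAP*

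**What the plan says.** Two kinds of success statement appear in the current text.

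- **Observed percentage.** Section 7.2.1 says: "The endpoint will be met if at least 90% of the treated" eyes rotate no more than five degrees. The synopsis item on success criteria for the primary effectiveness endpoint reads: "At least 90% of the treated eyes rotate less than or equal to five degrees between 18 and 24 months postoperative". Both add in parentheses that this means no more than 10% of eyes rotate by more than five degrees. Neither mentions a confidence limit or refers to section 7.5.
- **Confidence limit.** Section 7.5 says: "The null hypothesis will be rejected if the two-sided 95.0% upper confidence limit of the proportion of eyes with" more than five degrees of absolute rotation is at most 0.1, and adds: "An exact binomial confidence interval will be used". The statistical methods row of the synopsis gives the same limit rule.

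Section 7.1 sets the null at more than 10% of eyes failing and the alternative at 10% or fewer. Section 7.4 states: "A sample of 100 eyes provides 94.9% power to reject the null hypothesis that" more than 10% of eyes fail, with an assumed failure rate of 2% or less.

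**The concern.** The 90% sentence is phrased as a decision about treated eyes, and the synopsis lists it as the success criterion. The true proportion is never observed, so a reader can apply the sentence only to the observed percentage. Read that way, the endpoint can be declared met when the null hypothesis of section 7.1 has not been rejected.

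At stake is the primary conclusion of a study run as a condition of FDA approval (section 1.0). Suppose 93 of 100 eyes succeed. A report could cite section 7.2.1 and say the endpoint was met, although the upper limit for the failure proportion is 13.9% and the powered test has failed. The plan should not leave that choice open until the data are known.

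**Working it through.** **Inputs.** Null boundary 10% (7.1); planned failure rate 2% and 100 evaluable eyes (7.4); 124 enrolled primary eyes (7.4); exact two-sided 95% interval (7.5), taken as Clopper-Pearson. Complete data are assumed throughout. The 2% rate is the planned one, and 1% lies within the plan's 2% or less. All other failure rates below are assumptions that are not in the documents, chosen to show a range.

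**Formula.** With x failures in n eyes, the upper limit is the 0.975 quantile of a Beta(x + 1, n − x) distribution. The section 7.5 rule is met if this limit is ≤ 0.10. The literal section 7.2.1 rule is met if x/n ≤ 0.10.

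**Step 1: reproduce the plan's power.** At n = 100, the limit is 0.0993 for x = 4 and 0.1128 for x = 5, so section 7.5 allows at most 4 failures. P(X ≤ 4 | n = 100, p = 0.02) = 0.9492, which matches the stated 94.9%. The literal rule gives P(X ≤ 10 | n = 100, p = 0.02) > 0.9999, which does not. The study was therefore sized on section 7.5. Enrolment also reproduces: 100 / (0.9 × 0.9) = 123.5, rounded up to 124.

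**Step 2: where the rules disagree, n = 100.**

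| Failures | Upper 95% limit | 7.2.1 read literally | 7.5 |
|---|---|---|---|
| 4 | 0.0993 | met | met |
| 5 | 0.1128 | met | not met |
| 6 | 0.1260 | met | not met |
| 7 | 0.1389 | met | not met |
| 8 | 0.1516 | met | not met |
| 9 | 0.1640 | met | not met |
| 10 | 0.1762 | met | not met |
| 11 | 0.1883 | not met | not met |

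If all 124 primary eyes are evaluable, section 7.5 allows 5 failures (limit 0.0916; 6 failures give 0.1023). Literal 7.2.1 allows 12 (12/124 = 9.7%; limit 0.1629). They disagree at 6 to 12.

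**Step 3: chance of a result on which they disagree.** This is P(5 ≤ X ≤ 10) for 100 eyes and P(6 ≤ X ≤ 12) for 124 eyes.

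| True failure rate | 100 eyes | 124 eyes |
|---|---|---|
| 1% | 0.3% | 0.2% |
| 2% (planned) | 5.1% | 3.9% |
| 3% | 18.2% | 17.0% |
| 4% | 36.9% | 37.5% |
| 5% | 55.3% | 58.1% |

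**Step 4: chance of declaring success when the true rate lies inside the null.**

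| True failure rate | Eyes | 7.2.1 read literally | 7.5 |
|---|---|---|---|
| 11% | 100 | 45.3% | 1.1% |
| 12% | 100 | 33.4% | 0.5% |
| 11% | 124 | 38.5% | 0.5% |
| 12% | 124 | 26.2% | 0.2% |

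**The case against.** The strongest reply is that the plan has only one working decision rule. Section 7.2.1 names the target proportion, section 7.1 turns it into hypotheses, and section 7.5 says how they are tested. The parenthesis in 7.2.1 has the same content as the alternative hypothesis. Section 7.2.2 says "There are no pre-specified performance targets for the secondary endpoints", which suggests that the 90% is the corresponding target for the primary endpoint. If the literal reading were meant, the interval and the power calculation would have no role in deciding success. This is probably what the authors intended, and it is why the matter is one of wording and not of design. It does not supply the missing link, because the sentence that defines success still gives a different answer from the test.

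Three further points limit the size of the finding:

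- The pass rates at 11% and 12% belong to the literal reading. They are not error rates of the planned test.
- The larger disagreement figures use failure rates above the planned 2%. Within the plan's own assumption the chance of conflict is at most about 5%.
- Sections 7.3 and 7.6 make the ITT analysis with multiple imputation the main one, so the exact cut-offs may shift when data are missing. The gap between an observed-percentage rule and a confidence-limit rule remains.

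Parts of the synopsis methods row are redacted, so a linking sentence there cannot be ruled out. No redaction is visible in 7.2.1 or 7.5.

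**Conclusion.** The concern holds. Followed as written, section 7.2.1 and the synopsis success item can declare the endpoint met when section 7.5 does not reject the null. With 100 complete eyes this happens at 5 to 10 failures, and with 124 at 6 to 12. The chance of such a result is 5.1% or 3.9% respectively at the planned 2% rate, and it rises steeply if the true rate is higher. The intended rule is recoverable from the power figure, and the sample size and test are sound. The defect is confined to the sentences that define success, but it bears on the primary conclusion and should be corrected. The counts assume complete data and a Clopper-Pearson interval.

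**What to change.** Replace the success statement in section 7.2.1 and in the synopsis success-criteria item with wording such as:

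> The primary endpoint is met only if the null hypothesis is rejected by the rule in section 7.5, that is, if the upper limit of the exact two-sided 95% confidence interval for the proportion of eyes rotating more than 5° between 18 and 24 months does not exceed 0.1. The observed percentage of eyes rotating 5° or less is reported descriptively.

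The analysis sets and imputation in sections 7.3 and 7.6 are left as they stand. The cost is one paragraph and one synopsis item. Sample size, power, data collection and the test do not change.

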7.2.2 Secondary Endpoints

The following additional endpoints will be evaluated:

- Absolute rotation between visits.
- Absolute rotation <5 degrees, <10 degrees, <20 degrees, and <30 degrees from the intended orientation at each visit.
- Absolute rotation from the intended orientation at each visit.
- Postoperative manifest refraction spherical equivalent and cylinder at each visit.
- Ocular AE rates assessed in implanted eyes.

There are no pre-specified performance targets for the secondary endpoints.

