2.0 OBJECTIVE

The objective of this PAS is to evaluate the long term (i.e., 24 months) clinical performance of the TICL with respect to rotational stability, refractive and visual outcomes, and ocular adverse event (AE) rates.

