6.3 Reporting

6.3.1 On-Site Expedited Reporting

The Investigator is obligated to report the following to the Sponsor within 24 hours of becoming aware of the event to ensure the safety of all participants in the study and to meet regulatory reporting requirements:

- all **SAEs**, regardless of relationship to study device or study protocol
- all **non-serious AEs** determined to be related to the study device (ADE)
- all device malfunctions that do not result in one of the above reportable events
- all secondary surgical interventions (removal, replacement or repositioning) involving the study lens

When reporting these events to the Sponsor, the site should forward any supporting documents along with the appropriate reporting form and the corresponding CRF, if applicable. Refer to the Personnel and Facilities section for Sponsor contact information for reporting of SAEs/ADEs and device malfunctions. Sites must also report applicable events to the reviewing IRB per its established reporting procedures.

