- Retroilluminate the TICL with the illumination arm perpendicular to cornea
- Use appropriate slit beam width and height to achieve optimal retroillumination and image quality

Ensure that:

- TICL markings visible
 - TICL edge visible
 - Eye centered in image
 - Scleral/conjunctival blood vessels / iris architecture clearly defined
 - A secondary light source should be used to optimize visibility of iris and scleral/conjunctival blood vessels. This secondary illumination system needs to be set high enough to provide general illumination of the entire eye in addition to where the slit beam is present. The secondary illumination system can be controlled by twisting the top of the slit lamp where the illumination system is.
3. Images will be downloaded and submitted to an independent reading center for analysis of the rotation of the TICL for degrees of rotation between each visit and from intended axis placement.

4. Image Analysis

a) Determination of the intended TICL axis placement.

On the intraoperative images, the axis markings on the TICL will be identified and a lens-marking-line will be drawn. Landmarks in the iris, sclera, or conjunctiva, such as blood vessels and iris features, will be

identified. A landmark-line connecting these landmarks will be drawn. The difference in degrees between the lens-marking-line and landmark-line will be the intended TICL axis placement.

b) Postoperative TICL Orientation Assessment

On all images obtained at follow-up visits, a lens-marking-line will be drawn. The same landmarks used to determine the TICL axis placement on the intraoperative images will be marked and the landmark-line will be drawn.

The TICL axis orientation will be calculated as the difference in degrees between the lens-marking-line and the landmark-line.

Refer to section 7.2 Study Endpoints for the planned analyses.

REFERENCES

- ¹ Directions for Use, Visian® TORIC ICL (Implantable Collamer® Lens) for Myopia.
- ² Bailey IL, Lovie JE. New design principles for visual acuity letter charts. *Am J Optom Physiol Opt.* 1976 Nov; 53(11):740-5.
- ³ Recommended standard procedures for the clinical measurement and specification of visual acuity. Report of working group 39. Committee on vision. Assembly of Behavioral and Social Sciences, National Research Council, National Academy of Sciences, Washington, D.C. *Adv Ophthalmol.* 1980; 41:103-48.

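### The secondary rotation endpoints have no rule for eyes whose lens is surgically repositioned or exchanged, so the Month 24 rates mix lens stability with surgical correction

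*Combined protocol and SAP*

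**What the plan says.** The objective in section 2.0 is to "evaluate the long term (i.e., 24 months) clinical performance of the TICL with respect to rotational stability". Section 7.2.2 gives three secondary rotation endpoints: "Absolute rotation between visits", "Absolute rotation <5 degrees, <10 degrees, <20 degrees, and <30 degrees from the intended orientation at each visit", and "Absolute rotation from the intended orientation at each visit". The analysis in section 7.5 is: "Secondary endpoints, degrees of rotation between visits and misalignment from the intended orientation will be analyzed using descriptive statistics".

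Appendix B fixes the reference from the surgical images: "The difference in degrees between the lens-marking-line and landmark-line will be the intended TICL axis placement". For follow-up images, "The same landmarks used to determine the TICL axis placement on the intraoperative images will be marked", and orientation is read as the angle between the lens line and the landmark line.

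Lens surgery after implantation is expected. Section 6.1.1 lists removal, replacement and repositioning among the surgeries linked to this lens family. Section 6.3.1 requires a report to the sponsor within 24 hours of "all secondary surgical interventions (removal, replacement or repositioning) involving the study lens".

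The only rule for an eye after such surgery is in section 7.4. It covers explantation, and only in the primary analysis, where an enrolled and implanted fellow eye may take the explanted eye's place. Imputation in section 7.6 also covers only the primary endpoint.

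**The concern.** An endpoint read visit by visit against a fixed reference describes lens stability only while nobody moves the lens. Once a surgeon realigns or exchanges it, later readings reflect the operation as well as the lens. The eyes affected are likely to include those with the largest rotation, because rotation is a natural reason to operate.

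The primary endpoint covers months 18 to 24, a period for which section 7.1 assumes that rotation has largely settled. Measured rotation in degrees before month 18, and from surgery to Month 24, is reported through the secondary endpoints. A reader will take a Month 24 rate within 10 or 20 degrees as a statement about the lens. If it includes realigned eyes without marking them, it describes lens plus surgery.

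**Working it through.** **The plan's own figures.** With 100 eyes and an exact two-sided 95% interval, 4 failures give an upper limit of 0.0993 (at most 0.1, pass) and 5 give 0.1128 (fail). Power at a 2% failure rate is P(X ≤ 4 | n = 100, p = 0.02) = 0.949, as stated in section 7.4. Enrolment is 100 / (0.9 × 0.9) = 123.5, rounded up to 124, also as stated. None of these figures uses the secondary endpoints.

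**Following the rules for an eye with a lens intervention.** The 35 degrees below is a made-up value.

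1. *Repositioned after a scheduled image.* The Month 1 image reads 35 degrees, and the lens is returned to its axis before Month 3. Rotation between visits is |0 − 35| = 35 degrees, all of it the surgeon's move. Month 1 correctly shows 35 degrees. From Month 3 to Month 24 the eye is within 5 degrees, with no mark of what happened.
2. *Rotated and repositioned between scheduled images.* The lens rotates after the Day 5–9 image and is realigned at week 2, before the Week 3–5 image. Both images read near 0, so rotation between visits is near 0. Section 5.1.5 asks for documentation of unscheduled visits but not for a rotation image. The event is then known from the intervention report but not from the rotation endpoints.
3. *Exchanged.* Section 4.1 says that each lens may be turned up to 22.5 degrees either way to reach the planned axis, and that its markings do not show where the cylinder axis lies. Two correctly placed lenses can therefore have markings at different angles. Appendix B has no step for a new reference. If the first surgery's reference is kept, the difference between the two planned angles is scored as misalignment.
4. *Explanted or exchanged, then discontinued.* Section 3.2.3 allows this. The eye then leaves the secondary denominators, and its rotation is absent from the Month 24 rates.

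**Size, as an illustration.** The documents give no rate of repositioning or exchange. Assume that a proportion r of eyes is realigned for rotation, with r from 1% to 5%. Assume also that 100 eyes are seen at Month 24 (124 × 0.9 × 0.9 = 100.4), that the realigned eyes are among them, and that all other eyes are on axis. The as-written rate within 10 degrees is 100/100 (exact 95% CI 96.4% to 100%). The proportion on axis without surgery for rotation is (100 − 100r)/100:

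| r | On axis, no surgery for rotation | Exact 95% CI | Gap from 100% |
|---|---|---|---|
| 1% | 99% | 94.6% to 99.97% | 1 point |
| 2% | 98% | 93.0% to 99.8% | 2 points |
| 3% | 97% | 91.5% to 99.4% | 3 points |
| 5% | 95% | 88.7% to 98.4% | 5 points |

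The chance of at least one such eye among 124 is 1 − (1 − r)^124: 71% at r = 1%, 92% at 2%, 98% at 3% and 99.8% at 5%.

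**The case against.** **The endpoint is position at a visit.** A lens lying within 5 degrees at Month 24 is correctly described as such, whatever came before. Counting every re-operated eye as failing all thresholds would replace observed position with a composite, and would misstate an eye that rotated 12 degrees and never passed 20 or 30. This stands. The observed by-visit rates should stay, and the remedy is to show the affected eyes beside them. It does not excuse counting a surgeon's move as rotation between visits, or scoring a second lens against the first lens's reference.

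**A reader might infer that early rotation is hidden, or that these endpoints are the only evidence on it.** The documents do not support either reading. Appendix A schedules rotation assessment at surgery, Day 1–2, Day 5–9, Week 3–5 and on to Month 24, and each visit is reported. Lens interventions go to the sponsor within 24 hours, ocular adverse event rates are an endpoint, and manifest cylinder is measured from Day 5–9. Rotation goes unmeasured only when it arises and is corrected between two scheduled images. Even so, no repositioning or exchange rate is a named endpoint, and an event count does not give degrees.

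**A reader might infer that an exchanged lens will be mis-scored by up to 45 degrees.** That is 22.5 + 22.5, which needs two lenses at opposite ends of the allowance. It is a theoretical bound, not an expected size. Appendix B does not say that the first surgery's images must be used after an exchange, and the eye may be discontinued instead. What remains is that the plan does not settle the matter.

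**No decision depends on these endpoints.** They have no targets, and section 7.7 disclaims any claims for them. This stands and limits the weight of the point.

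**Conclusion.** The point holds as a gap in endpoint definition with a foreseeable effect on interpretation. The secondary rotation endpoints and the image-analysis method apply unchanged to repositioned and exchanged eyes. Surgical movement is then recorded as rotation, realigned eyes enter later rates unmarked, and an exchanged lens that stays in the study may appear falsely rotated.

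On an assumed 1% to 5% realignment rate, the Month 24 rate exceeds the rate of eyes that stayed on axis without surgery by 1 to 5 points. This assumes that every such intervention was for rotation and that the eyes remain in follow-up. The documents support neither the rate nor the cause, so the range only illustrates scale. An exchanged lens would push the error the other way.

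The primary decision rule, the 94.9% power and the 124 subjects are untouched. The change is worth making, but the trial's main conclusion does not rest on it.

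**What to change.** Amend sections 7.2.2 and 7.5 and Appendix B before data lock:

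1. Exclude from rotation between visits any pair of visits that spans a lens repositioning or exchange.
2. Present positions after a lens intervention separately, against a new reference taken from the re-intervention images where these exist. Do not pool them with eyes whose lens was not touched.
3. Keep the observed by-visit rates. Beside them, report the cumulative proportion of eyes through Month 24 with rotation above each threshold (using the last image before any intervention) or with lens surgery for rotation. Show the two components in separate rows, so that an eye that never passed a threshold is not described as having done so.

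The images and intervention reports needed are already collected, and no added procedure is required. The reason for surgery would come from the intervention report and its supporting documents, which assumes that it is recorded there. The cost is a few lines of text and a few extra table rows, and the secondary results may look slightly less favourable. Sample size and the primary analysis stay as they are.
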